10.1.1.2.2. Part B

All Target Engagement parameters in Part B will be calculated using a model based post-hoc analysis and the currently supported version of NONMEM. The model based post-hoc analysis is described in Section 11. All calculations will be based on actual sampling times.

Target Engagement parameters that will be calculated for free CCL17 in Part B are listed

CCI

CCI

[figure not shown]
NOTES:

Additional parameters may be included as required.

¹In the event that a robust and predictive population PK/TE model cannot be developed e.g. data limited by high levels of NR data, TE parameters will be derived directly from the observed data.

Target engagement parameters that will be calculated for total CCL17 in Part B are listed below. Additional parameters may be included as required.

CCI

NOTES:

Additional parameters may be included as required.

¹In the event that a robust and predictive population PK/TE model cannot be developed e.g. data limited by high levels of NR data, TE parameters will be derived directly from the observed data.

10.1.2. Summary Measure

Individual and median/mean concentration-time profiles of Free and Total CCL17 (stratified by treatment group in Part A) will be plotted and listed. Free and Total CCL17 concentrations in serum will be summarized descriptively.

Derived serum TE parameters will be summarised using descriptive statistics, graphically presented (where appropriate) and listed.

10.1.3. Population of Interest

The target engagement analyses will be based on the Safety population, unless otherwise specified.

10.1.4. Strategy for Intercurrent (Post-Randomization) Events

[figure not shown]
Missing data will not be imputed, regardless the reasons.

10.1.5. Statistical Analyses / Methods

Details of the planned displays are presented in [Appendix 11](#) and will be based on GSK Data Standards and statistical principles.

Unless otherwise specified, endpoints / variables defined in Section [10.1.1](#) will be summarised using descriptive statistics, graphically presented (where appropriate) and listed.

cci

The within subject and timepoint blister fluid:serum concentration ratio for free and total CCL17 may be determined from the concentration-time data if data permit. The free and total CCL17 concentrations will be summarised using descriptive statistics, graphically presented (where appropriate) and listed.

10.3. Immunogenicity

10.3.1. Summary Measure

The number and percentage of confirmed positive samples in each treatment group will be presented at each time assessed. Only binding antibody detection is collected in this study. Neutralising antibody detection is not collected.

10.3.2. Population of Interest

The immunogenicity analyses will be based on the safety population, unless otherwise specified.

For the in-stream safety reviews 1 and 2, subject data will be anonymised as outlined in [Appendix 6](#)

11. PHARMACOKINETIC / TARGET ENGAGEMENT / PHARMACODYNAMIC (PK/TE/PD) ANALYSES

The primary goal of this analysis is to characterize the Pharmacokinetic / Target Engagement (PK/TE) relationship of GSK3858279 following IV and SC administration to healthy and OA participants. The influence of subject demographics and baseline characteristics, including disease activity, may be investigated. PK and TE data will be analysed using the currently supported version of NONMEM. Details of this analysis are described in a separate RAP [GSK Document number [TMF-14343601](#)].

The relationship between Pharmacokinetic / Target Engagement / Pharmacodynamic (PK/TE/PD) of GSK3858279 following repeat SC administration to OA participants may also be explored. Details of this analysis are described in a separate RAP GSK Document number [TMF-14343601](#).

11.1. Pharmacokinetic / Target Engagement / Pharmacodynamic Dataset Specification

The dataset specification to support any PK/TE/PD analysis will be provided as a separate document.

The merging of PK, TE, treatment, demographic and efficacy data together with the creation of the NONMEM-specific dataset will be performed by, or under the direct auspices of, Clinical Statistics & Programming, GSK.

This dataset programming will be conducted in a HARP environment using the currently supported version of SAS.

12. BIOMARKER ANALYSES – PART A ONLY

12.1. Immune Cell Phenotypes

CCI

12.1.2. Summary Measure

Two summary measures are of interest, the treatment effect (Placebo vs GSK3858279) and the difference between sample types (Blood vs Blister).

- Mean Treatment Difference in Change from baseline at all visits
- The within subject and timepoint ratio of Blister:Blood at all visits – only for blister induced cohorts of Part A

Measures of sample reliability (Blister Volume and Total White Blood Cell Count) will be listed only.

CCI

12.1.4. Statistical Analyses / Methods

Details of the planned displays are provided in [Appendix 11](#) and will be based on GSK Data Standards and statistical principles.

Unless otherwise specified, endpoints / variables defined in Section [10.1.1](#) will be summarised using descriptive statistics, graphically presented (where appropriate) and listed.

12.1.4.1. Statistical Methodology Specification

Endpoint / Variables

 Percentage of Immune Cell Phenotypes
Model Specification

 Endpoints will be analyzed for each flow cytometry cell type using generalized linear mixed models (GLMM) with appropriate link functions or transformations performed as required. Terms in GLMM model will include: 
 categorical: baseline, treatment group, sample type, visit and two 3-way interactions 
 baseline with sample type with treatment group visit with sample type with treatment group Random effect: subject The Kenward and Roger method for approximating the denominator degrees of freedom and correcting for bias in the estimated variance-covariance of the fixed effects will be used. An unstructured covariance structure for the R matrix will be used by specifying 'type=UN' on the RANDOM line. 
 In the event that this model fails to converge, alternative correlation structures may be considered such as CSH or CS. Akaike's Information Criteria (AIC) will be used to assist with the selection of covariance structure. LS Means for the Sample Type by Treatment by Visit will be calculated using the observed baseline mean for each sample type separately.
Model Checking & Diagnostics

 Distributional assumptions underlying the model used for analysis will be examined by obtaining a normal probability plot of the residuals and a plot of the residuals versus the fitted values (i.e. checking the normality assumption and constant variance assumption of the model respectively) to gain confidence that the model assumptions are reasonable. If there are any departures from the distributional assumptions, alternative models will be explored using appropriate transformed data.
Model Results Presentation

For summary measure 1 (mean treatment difference), for each sample type and each treatment group:
 
 Number of subjects in analyses Least Squares Mean of Change from Baseline with Standard Error 
For all GSK3858279 arms
 
 Difference to Placebo, 95% Confidence Interval and p-value In addition for 3 mg SC: Difference to 3mg IV, 95% Confidence Interval. 
For summary measure 2 (Mean Sample Type Difference), for each treatment group and overall (see note) and each sample type:
 
 Number of subjects in analyses Least Squares Mean of Change from Baseline with Standard Error 
For Blister
 
 Difference to Blood, 95% Confidence Interval

Note: overall (treatment-independent) mean will be calculated for Blister and Blood, for each visit.

Plots of LS Means (+/- SE) and Difference (95% CI) will be presented.

Sensitivity and Supportive Analyses

- A characterisation of the dose and/or exposure response may be carried out if data allows.

CCI

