1.1. Version history

SAP Version	Approval Date	Protocol Version (Date) on which SAP is Based	Change	Rationale
SAP	01-MAR-2021	2017N342035_05 (07-SEP-2020)	Not Applicable	Original version.
SAP amendment 1	01-JUN-2021	2017N342035_05 (07-SEP-2020)	Part B sections	Part A, unmodified from previous version, and amended Part B.
SAP amendment 2	24-MAR-2022	TMF-14447953 (09-FEB-2022)	Part B Sections Programming notes for PK and TE outputs Adding additional Interim Analyses Information	Protocol was amended to account for two additional Interim Analyses.
SAP Amendment 3	28-JUL-2022	TMF-14447953 (09-FEB-2022)	Primary model update. Clarification on Intercurrent Events section. Additional outputs for IA4 and Part B SAC. Inclusion of safety tables (Part B 2.37-2.39)	Update to the model specification to avoid overparameterization by removal of the random subject intercept, and to include only data during the treatment period (i.e. up to week 8) in the primary analysis model. (Section 7)

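### The Part A immune-cell model lists baseline as categorical but computes LS means at the baseline mean; coded as a class factor, the comparisons with placebo are not estimable

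*SAP*

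**What the plan says.** SAP 12.1.4.1 analyses "Percentage of Immune Cell Phenotypes" with a generalised linear mixed model, fitted separately for each cell type. The listed terms are "categorical: baseline, treatment group, sample type, visit and two 3-way interactions". The first interaction is "baseline with sample type with treatment group"; the second replaces baseline with visit. The list has no line for continuous terms.

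On LS means, the section says: "LS Means for the Sample Type by Treatment by Visit will be calculated using the observed baseline mean for each sample type separately".

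On covariance, it gives "Random effect: subject" and also "An unstructured covariance structure for the R matrix will be used", requested through the type option of the RANDOM statement. CSH or CS may be considered if the model does not converge, with AIC to help choose.

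For each active arm the required output is "Difference to Placebo, 95% Confidence Interval and p-value". The blister-versus-blood comparison has a confidence interval but no p-value. The results go to Tables 5.02 and 5.03 and Figures 5.01 to 5.04 (SAP 14.11.12 and 14.11.13).

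The Part B repeated-measures models (SAP 7.1.5.1 and 7.2.5.1) list baseline separately as continuous.

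**The concern.** A cell percentage takes almost as many values as there are participants. If it enters as a class factor, each baseline level belongs to one participant and sample type, or to very few. The factor then absorbs the differences between participants. Treatment was assigned between participants, so the treatment effect is absorbed too.

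The LS-means sentence treats baseline as a number with a mean. The two instructions cannot both be followed, and the SAP does not say which governs. A programmer who follows the term list literally would get non-estimable results for the comparisons that the section asks for, and someone would then have to change the model after unblinding. What is at stake is the set of Part A immune-cell treatment differences with their intervals and p-values.

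**Working it through.** The section gives no sample size or error rate, so there is no plan figure to reproduce. The check is one of estimability.

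**Inputs**
- Blister cohorts: 1, 3 and 10 mg/kg IV, and SC (Protocol 1.3.3 and 1.3.4), so 4 cohorts.
- Cohort size: 8, as 6 active and 2 placebo (Protocol 4.2). Total 4 × 8 = 32 participants: 24 active and 8 placebo. Placebo is one pooled group (SAP 5.2), which gives 5 treatment groups.
- Sample types: 2 (blood, blister).
- Post-baseline visits: 2 per participant, Day 8 and a last blister visit. The last visit is first treated as the same nominal visit in all cohorts.
- Rows: 32 × 2 × 2 = 128.
- Assumptions: complete data; simulated baseline values, distinct for each participant and sample type, then coarsened to show a range.

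**Rule.** A contrast with coefficient vector L is estimable only if L lies in the row space of the design matrix X, that is, if adding L as a row leaves rank(X) unchanged.

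**Contrasts needed.** 4 active arms × 2 sample types × 2 visits = 16.

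**Baseline as a class factor, distinct values.** There are 32 × 2 = 64 levels, one for each participant and sample type. They saturate every mean at that level. All that remains is one change between visits for each treatment and sample type: 5 × 2 = 10. The rank is 64 + 10 = 74, and no information is left on the treatment level itself.

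**Baseline continuous, same interactions.** There are 5 × 2 × 2 = 20 cell means and 5 × 2 = 10 slopes, so the rank is 30.

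| Baseline coding | Levels | Active-vs-placebo contrasts estimable |
|---|---|---|
| Class, distinct values | 64 | 0 of 16 |
| Class, coarsened | 37–40 | 0 of 16 |
| Class, coarsened | 13 | 0 of 16 |
| Class, coarsened | 4 | 2 to 4 of 16 |
| Class, coarsened | 2 | 14 to 16 of 16 |
| Continuous | – | 16 of 16 |

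The entries for coarsened baselines depend on the simulated values. Under the class coding with distinct values, the 4 × 2 = 8 differences between treatment and placebo in change between visits remain estimable, but these are not the contrasts that the SAP requests.

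**Unequal last visit.** The last blister visit is Day 43 in the 1 mg/kg cohort and Day 29 in the others. Treated as separate visits, there are 4 × 2 × 3 = 24 nominal contrasts, of which 8 are empty cells under either coding. The other 16 are all estimable with continuous baseline; with distinct class levels none is.

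**Covariance.** Each participant has 2 × 2 = 4 responses, so an unstructured matrix has 4 × 5 / 2 = 10 parameters. A random intercept makes 11 parameters for 10 distinct moments (rank 10): one is redundant. Under the CS fallback, a random intercept makes 3 parameters with rank 2. To test whether this matters for the contrasts, one marginal covariance was split with a random-intercept variance of 0, 0.5 and 1.0. A generalised least squares contrast was the same each time (0.4196, SE 2.245).

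**The case against.** The best defence is that the section should be read as a whole. Setting baseline at its mean makes sense only for a covariate, and the Part B models list it as continuous. Those Part B models also place a baseline-by-week interaction under their categorical heading, which suggests that the heading is used loosely. A competent programmer would probably code baseline as continuous, and every contrast is then estimable. This is fair, and it limits the finding to a contradiction in the specification. It does not remove the finding: the term list still states the wrong type, and nothing in the section says that the LS-means sentence overrides it.

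A reader might go further in three ways that the documents do not support.

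- **That the random subject effect with unstructured R also makes the contrasts non-estimable.** It does not. At most one parameter is redundant, which may hinder convergence but leaves contrasts and standard errors unchanged for a given marginal covariance. The text may also describe a single RANDOM statement in which subject is only the blocking unit, and then nothing is redundant. The SAP 1.1 entry on Amendment 3, "Update to the model specification to avoid overparameterization by removal of the random subject intercept", concerns the Part B Bayesian pain model and does not show that a subject term is wrong here.
- **That any convergence fix would be arbitrary.** The section already names the trigger, the alternative structures and AIC.
- **That the trial's main conclusions are at risk.** This is a Part A biomarker model, and no visible objective or decision rule uses it.

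The endpoint and population text of SAP 12.1 is redacted, so 32 is planned enrolment in the blister cohorts and not a confirmed analysis set.

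**Conclusion.** Wrong as written. The term list makes baseline categorical, while the LS-means rule in the same section needs it continuous. Followed literally, the list leaves none of the 16 required active-versus-placebo LS-mean differences estimable; with baseline continuous, all 16 are. The zero does not require every baseline to be unique, since it persists down to about 13 levels. It does rest on planned enrolment, complete data, two post-baseline visits and simulated baselines.

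Non-estimability comes from the categorical coding alone. The covariance wording is a secondary point of clarity. The effect is confined to the Part A immune-cell analysis, where only the treatment differences carry p-values.

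**What to change.** In SAP 12.1.4.1, move baseline to its own line as a continuous covariate and keep both three-way interactions. The LS-means sentence can then stand unchanged.

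As a secondary clarification, state one covariance specification: either unstructured R alone with the existing CSH or CS fallback, or a random subject effect with a simple residual. Either is valid.

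The text change is a few words and needs no new data. The SAP allows Part A to be reported before Part B ends, and the documents do not show whether this model has already been run. If it has, the sponsor should record which coding and covariance were fitted, and rerun the analysis only if baseline was entered as a class factor.

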14. APPENDICES

14.1. Appendix 1: Protocol Deviation Management and Definitions for Fully Treated Population

14.1.1. Exclusions from Fully Treated Population (Part A) and Per Protocol Population (Part B)

Part A: A participant meeting any of the following criteria will be excluded from the Fully Treated population:

Exclusion Description
Patient did not receive $\geq 80\%$ of planned medication*

*Part A has a single dose. Percentage of actual amount administered will be derived using the planned dose and the injected infusion volume. In case a subject didn't receive a full dose in PART A, the actual amount of drug administered (AMT) will be calculated as AMT [mg]= numerical part of treatment group [mg/kg] * WTBL [kg] * percentage of infusion volume / 100 when EXPOSURE.ACTTRT is "GSK3858279". In case a subject from the 3 mg/kg SC treatment group didn't receive a full dose and WTBL ≥ 80 kg, then AMT [mg]= 240 [mg] * percentage of infusion volume / 100. The percentage of infusion volume (TVOLPCT) is assumed 100 for a full dose.

Part B: A participant who meets any of the below criteria will be excluded from the Per Protocol population:

Violation Category	Criterion Violated	Deviation
Inclusion/Exclusion Criteria	Inclusion Criteria No. 7	Did not have OA of the index knee as defined by symptoms for ≥ 6 months with a clinical diagnosis of OA as per American College of Rheumatology (ACR) clinical diagnosis criteria
	Inclusion Criteria No. 8	Did not have an average of daily pain score ≥ 4 and ≤ 9 by the 11-point NRS (0-10) in index knee over 7 days prior to dosing (Day-7 to Day-1). Data should be recorded on at least 5 of 7 occasions by the participant to obtain a valid baseline value.
	Inclusion Criteria No. 9	Did not have a Kellgren and Lawrence (KL) score ≥ 2 on X-ray obtained during screening (Kellgren, 1957).
	Exclusion Criteria No. 39	Diagnosis of current inflammatory arthritis such as rheumatoid arthritis, autoimmune disorder affecting joints, seronegative spondyloarthritis, gout or pseudogout in any joint (defined as acute episodic attacks of swollen, painful joint in a patient with X-Ray chondrocalcinosis or calcium pyrophosphate dihydrate [CPPD] crystals). Note: asymptomatic CPPD crystals on X-ray are not an exclusion
	Exclusion Criteria No. 67	Underwent intra-articular therapy within 3 months prior to signing the informed consent.
	Exclusion Criteria No. 68	Intake of Immunosuppressants, including corticosteroids (parenteral within 3 months of screening; oral within 1 month of screening).
Prohibited Medications*		Any use of Systemic Corticosteroids from screening until the end of Week 8

Violation Category	Criterion Violated	Deviation
CC1		Any use of Intra-articular therapy of the index joint from screening until the end of Week 8
		Any use of, opioids, NSAIDs, topical analgesics or anti-neuropathic agents 24 hours before a clinical visit on more than 1 visit during the first 8 weeks (Day 1 – Day 57)
		Any use of opioids, NSAIDs, topical analgesics or anti-neuropathic agents for more than 1 day per week on more than 1 visit during the first 8 weeks (Day 1 – Day 57)
Study Medication		Missing more than 1 dose out of 8 doses of study treatment
Missing Diary Data		Missing average knee pain or worst knee pain diary data for more than 2 days per week in more than 1 week out of the first 8 weeks (Day 1 – Day 57)
		Missing rescue medication (paracetamol) diary data for more than 2 days per week in more than 1 week out of the first 8 weeks (Day 1 – Day 57)

*Where medications listed above need to be identified programmatically, a list of dictionary codes from the GSK Drug dictionary will be defined with input from the study physician and coding dictionary analyst. The list will be created prior to unblinding and stored in a spreadsheet in refdata.

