- 66. Treatment with biologic agents (such as monoclonal antibodies including marketed drugs) within 3 months or 5 half-lives (whichever is longer) prior to dosing.
- 67. Intra-articular therapy within 3 months prior to signing the informed consent.
- 68. Immunosuppressants, including corticosteroids (parenteral within 3 months of screening; oral within 1 month of screening).
- 69. Unable or unwilling to discontinue all pain medication including topical analysesic or adjunctive treatment as per Section 6.5 and Section 6.6.
- 70. Major surgery (as per investigator's judgement) within 3 months prior to dosing.

PRIOR/CONCURRENT CLINICAL STUDY EXPERIENCE

- 71. Participation in the study would result in loss of blood or blood products in excess of 500 mL within 56 days.
- 72. Exposure to more than 4 new chemical entities within 12 months prior to the dosing day.
- 73. Current enrolment or past participation in a clinical study of an investigational drug intervention within the last 3 months or 5 half-lives (whichever is longer) of signing consent.

DIAGNOSTIC ASSESSMENTS

- 74. Positive HIV antibody test.
- 75. Presence of HBsAg at screening.
- 76. Presence of HBcAb at screening
- 77. Positive Hepatitis C antibody test result.
- 78. NOTE: Participants with positive Hepatitis C antibody due to prior resolved disease can be enrolled, only if a confirmatory negative Hepatitis C RNA test is obtained
- 79. Positive Hepatitis C RNA test result at screening or within 3 months prior to first dose of study intervention
- 80. NOTE: Test is optional and participants with negative Hepatitis C antibody test are not required to also undergo Hepatitis C RNA testing.
- 81. Positive coronavirus (COVID-19: SARS-CoV-2 PCR test of a combined throat and nasopharyngeal swab).

- 82. Clinically significant abnormal echocardiogram at screening, as assessed by the investigator.
- 83. Cardiac troponin or NT-proBNP levels out of normal range at screening.
- 84. A positive pre-study drug/alcohol screen at screening

OTHER EXCLUSIONS

- 85. Regular alcohol consumption within 6 months prior to signing the informed consent defined as:
 - an average weekly intake of >14 units for males and >14 units for females.
 - One unit is equivalent to 8 g of alcohol: a half-pint (~240 mL) of beer, 1 glass (125 mL) of wine or 1 (25 mL) measure of spirits.
- 86. Regular use of known drugs of abuse

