6.6. Prohibited Medications

The following are prohibited from Day -7 until Day 71. A washout period is required prior to Day -7, consisting of 3 days or 5 half-lives, whichever is longer. Refer to Figure 5.

- All pain medications including anti-neuropathic agents (e.g. Gabapentin and Pregabalin), opioids, NSAIDs, topical analgesics
- Adjunctive therapies

The following are prohibited throughout the entire duration of the study:

- Attenuated live vaccine(s)
- Biologic agents (monoclonal antibodies, therapeutic proteins)
- Antiplatelet or anticoagulant agents
- Immunosuppressants
- Systemic Corticosteroids
- Intra-articular therapy of the index joint

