5.3. Baseline Definitions

The baseline value will be the latest pre-dose assessment with a non-missing value, including those from unscheduled visits. If time is not collected, Day 1 assessments are assumed to be taken prior to first dose and used as baseline. Replicate assessments at a timepoint will be averaged, and the mean value will be used. Unless otherwise stated, if baseline data is missing, no derivation will be performed and baseline will be set to missing.

For the average and worst knee pain intensity, the mean of the scores in index knee over 7 days prior to dosing (Day -7 to Day -1) will be considered as baseline. Baseline should be calculated only if pain scores are recorded on at least 5 days out of 7. If pain scores are not recorded on at least 5 days, the baseline will be set to missing.

For Part B of the study, the CCL17 levels (free, total) baseline value will be derived by averaging the two pre-dose measurements (i.e., average of Day-4 and Day 1).

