7.1.4. Strategy for Intercurrent (Post-Randomization) Events

There is one intercurrent event that is of interest:

1. Treatment Withdrawal (Participant discontinues the study treatment but continues to stay in the study)

No imputations would be carried out if there are missing data due to intercurrent events.

A hypothetical strategy will be used to estimate what the treatment effect would have been had the subject not experienced the intercurrent event. Data collected after the occurrence of the Intercurrent Event will be listed but not used in summary stats and stats analysis TFLs. Since the dosing interval in this study is 7 days, the date of occurrence of the treatment withdrawal intercurrent event will be defined as the date of the first missed dose of study treatment i.e. date of last dose of study treatment + 7 days. Pain scores are measured daily in the evening, therefore pain scores on or after the date of last dose of study treatment + 7 days will be considered as occurring after treatment withdrawal.

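### On the visible text, the Per Protocol analgesic rules omit the baseline week and need more than one breaching visit, so prohibited analgesic use throughout the baseline week, or through most of Week 8, need not exclude a participant

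*SAP*

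**What the plan says.** **Prohibition.** Protocol 6.6 opens its first list with "The following are prohibited from Day -7 until Day 71". The list covers "All pain medications including anti-neuropathic agents (e.g. Gabapentin and Pregabalin), opioids, NSAIDs, topical analgesics". Exclusion No. 69 (Protocol 5.2) bars anyone "Unable or unwilling to discontinue all pain medication".

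**Endpoint weeks.** For both knee-pain endpoints, SAP 5.3 states that "the mean of the scores in index knee over 7 days prior to dosing (Day -7 to Day -1) will be considered as baseline". SAP 14.3 defines Week 8 as Days 50 to 56 and uses all diary data available in that interval.

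**PP rules.** SAP 14.1.1 has two analgesic rules for Part B:
- Rule 1 concerns use "24 hours before a clinical visit on more than 1 visit during the first 8 weeks (Day 1 – Day 57").
- Rule 2 reads "Any use of opioids, NSAIDs, topical analgesics or anti-neuropathic agents for more than 1 day per week on more than 1 visit", over the same Days 1-57.

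In the same table, the systemic corticosteroid and intra-articular rules act on any use from screening to the end of Week 8. The eligibility criteria listed as PP exclusions are Nos. 7, 8, 9, 39, 67 and 68. No. 69 is not among them.

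**Primary analysis.** The population is intent-to-treat (SAP 7.1.3). SAP 7.1.4 says "There is one intercurrent event that is of interest", namely treatment withdrawal. The PP model is fitted only if PP makes up 50 to 90% of ITT (SAP 7.1.5.1).

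**The concern.** Each co-primary endpoint contrasts two diary weeks, and the protocol's prohibition covers both. A score recorded under a prohibited analgesic enters the ITT model as observed, because only treatment withdrawal is handled as an intercurrent event. The sensitivity entry in SAP 7.1.5.1 points to 14.9.2, which contains seeds, priors and MCMC diagnostics. No subgroup analysis is planned. That leaves the PP run as the only visible analysis that could take these scores out.

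Its analgesic rules are not tied to the two weeks that form the endpoint. They start after the baseline week ends, and they count repeated breaches anywhere in Days 1-57. If use falls mainly in the baseline week, or only in Week 8, the PP result can carry the same altered scores as the ITT result. Agreement between the two would then look more reassuring than it is.

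**Working it through.** The plan states no figure on this point, so the check applies the rules to the calendar.

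**Inputs**
- Clinic visits in Days 1-57 (SAP 14.2.5): Days 1, 2, 5, 8, 15, 22, 23, 26, 29, 36, 43, 50, 51, 57.
- Study weeks (SAP 14.3): Week 8 is Days 50-56.
- Assumption A: use in the 24 hours before a visit means use on the preceding calendar day.
- Assumption B: *visit* in Rule 2 means study week, because the SAP model description writes week and visit as equivalents.

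A participant leaves PP if Rule 1 counts more than one visit, or Rule 2 counts more than one week with more than one use day.

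| Days of use | Rule 1 visits | Rule 2 weeks | Excluded from PP? |
|---|---|---|---|
| -7 to -1 | 1 (Day 1) | 0 | No |
| 51-56 | 1 (Day 57) | 1 | No |
| 50-55 | 1 (Day 51) | 1 | No |
| 52-56 | 1 (Day 57) | 1 | No |
| 51-55 | 0 | 1 | No |
| 50-56 | 2 (Days 51, 57) | 1 | Yes |
| -7 to -1 and 51-55 | 1 (Day 1) | 1 | No |
| -7 to -1 and 51-56 | 2 (Days 1, 57) | 1 | Yes |

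**Baseline week.** No day before Day 1 can count under Rule 2. Only Day -1 can count under Rule 1, and only once. Seven days of use therefore never exclude a participant by themselves.

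**Week 8.** With use confined to Days 50-56, Rule 2 reaches at most one week. Rule 1 reaches two visits only if both Day 50 and Day 56 are use days. The number of excluded patterns with k use days is therefore C(5, k-2):
- 4 days: 35 - 10 = 25 of 35 stay in PP.
- 5 days: 21 - 10 = 11 of 21 stay.
- 6 days: 7 - 5 = 2 of 7 stay (Days 51-56 and Days 50-55).
- 7 days: 1 - 1 = 0 of 1 stay.

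Altogether 25 + 11 + 2 + 0 = 38 of the 64 patterns with at least four use days stay in. This counts patterns, which are not equally likely, so it is not a probability.

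**Sensitivity to the reading.** If same-day use before a visit also counts under Rule 1, Days 51-56 reach two visits (51 and 57), as do Days 50-55 (50 and 51), and both are excluded. Days 52-56 still stay in, with one visit. If *visit* in Rule 2 means clinic visit, some Week 8 patterns could also be excluded. The baseline-week result is the same under all of these readings.

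**The case against.** **Redaction.** SAP 4.2 lists the Part B deviation categories as prohibited medications, rescue medications, study medication and missing diary data. In the 14.1.1 table a redaction mark sits where the rescue category would come. A hidden row or wording cannot be ruled out. This stands, and it limits the point to the visible text.

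**Upstream safeguards.** Exclusion No. 69, the washout before Day -7, the Day 1 eligibility re-check, the ban on waivers and the drug screens all make baseline-week use less likely. Inclusion No. 10 requires insufficient relief from, intolerance of or contraindication to oral NSAIDs. This stands as a reason to expect few cases. None of it removes a breaching participant's data.

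**Baseline use is not arm bias.** It precedes randomisation on Day 1, and the model adjusts for baseline and baseline by week. This stands: the result is mainly noise in the treatment contrast. Week 8 use is different, because it follows randomisation and could differ by arm.

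**Use is reported.** Important deviations are summarised and listed, and Table 1.26 summarises osteoarthritis medication over the SAP's Day -7 to Day 71 phase. This is true, but a descriptive table does not take scores out of a model.

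**Stronger inferences.** A reader might infer that the gap lowers the stated 75% chance of a positive conclusion at a true difference of 1. The documents do not support that: they give no rate of prohibited use, the efficacy analyses rest on ITT, and changing PP membership leaves ITT as it was. A reader might also infer that the rules discard harmless deviators, such as someone with two use days in each of Weeks 2 and 3. Those weeks are modelled jointly with Week 8 and reported, so harmless is too strong. The rules simply ignore where in the eight weeks the use falls.

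**Conclusion.** The gap is real on the visible text and modest in consequence. The baseline-week part is firm: use on all seven days of Day -7 to -1 never excludes a participant by itself, although Protocol 6.6 prohibits it and the steroid and intra-articular rules in the same table start at screening. The Week 8 part is conditional. Under assumptions A and B, use on up to six of the seven days can leave a participant in PP. It would be wrong to extend this to all of Week 8, because daily use on Days 50-56 is caught.

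No size of effect on the treatment difference can be given from the documents. The primary ITT result and its chance of a positive conclusion are unaffected by correcting the PP rules. What improves is the one visible, conditional, supportive analysis able to remove analgesic-modified scores. This is a cheap improvement.

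**What to change.** In SAP 14.1.1, before unblinding:

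1. Extend the PP analgesic criteria to the baseline week: exclude for prohibited analgesic use on more than 1 day in Day -7 to -1.
2. Add Exclusion No. 69 to the eligibility criteria that exclude from PP.
3. Add a criterion for prohibited analgesic use on more than 1 day in Days 50-56, whatever happens in other weeks.
4. Keep the two existing rules, and state whether *visit* means study week or clinic visit.

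The cost is SAP wording and programming. Medication dates are already needed for the Prohibited Medication Phase (SAP 14.4.1.1), and SAP 14.1.1 already requires the drug-code list before unblinding. The PP population becomes somewhat smaller, which also bears on the 50 to 90% condition for running the model. The Week 8 criterion is a post-randomisation exclusion that could remove more participants from one arm than the other. The existing PP rules share that weakness, so PP should stay supportive only.
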